16.2.2 Aim 2 Study Objectives

Primary Objective (Aim 2):

To utilize day 0 plasma measurements of vascular injury (permeability, vascular activation, coagulopathy/fibrinolysis, and glycocalyx degradation), altered damaged associated molecular pattern (DAMP) signaling, and indicators of sarcopenia and/or neuronal injury to test association with 60-day mortality (primary objective), organ failure free days (secondary objective), and individual organ-specific outcomes (ventilator free days, vasopressor-free days, dialysis-free days; secondary).

Exploratory Objectives (Aim 2):

1. To determine reproducible multi-marker plasma phenotypes of immune activation, vascular injury, DAMP activation, and sarcopenia/neuronal injury and test for association with 60-day survival (primary), organ failure free days (secondary), and individual organ-specific outcomes (VFD, vasopressor-free days, dialysis-free days)
2. To test whether the association between multi-marker plasma phenotypes and 60-day mortality is modified by classically defined syndromes (ARDS, pneumonia, and sepsis).
3. To test whether day 0 plasma measurements of vascular injury (permeability, vascular activation, coagulopathy/fibrinolysis, and glycocalyx degradation), altered damaged associated molecular pattern (DAMP) signaling, and indicators of sarcopenia and/or neuronal injury associate with for patient-reported health states (cognitive, emotional, functional, or respiratory) at 3, 6, and 12 months.
4. To test whether multi-marker plasma phenotypes early during the APS illness have predictive utility for patient-reported health states at 3, 6, and 12 months post-APS, specifically in cognitive, emotional, physical function, and respiratory domains.
5. To test whether a change in multi-marker plasma phenotypes between acute illness and 90 days associates with improved patient-reported health states at 3, 6, and 12 months.

16.2.3 Aim 2 Study Population

All participants enrolled in the APS Consortium will be eligible to participate in this aim. Our analytic plan, as detailed below, calls for a sample size of 1500 individuals at day 0 to test associations of both individual markers and patterns of co-expression of multiple plasma analytes while retaining adequate power to test for effect modification by APS state (ARDS, pneumonia, and sepsis). The 1500 subset for this profiling will be drawn from the first 2200 participants enrolled to allow for balance of demographic features, geographic areas, and APS states.

16.2.4 Aim 2 Study Design

Prospective observational cohort study with scheduled blood sampling, and longitudinal follow-up at 3, 6, and 12 months after critical illness.

16.2.5 Aim 2 Study Procedures

We will quantify the following proteins in plasma: Syndecan-1, angiotensin-2, soluble ICAM, soluble thrombomodulin, growth differentiation factor 15, soluble RAGE, S100A12, neurofilament light chain, and tau protein using multiplex electrochemiluminescence, conventional enzyme-linked immunosorbent assay (ELISA), or other automated multiplex immunoassay platforms (Simoa and/or ELLA). We will also quantify cell free DNA and mitochondrial DNA in plasma using Qiagen DNeasy miniprep kits and then quantitative polymerase chain reaction (qPCR) to quantify ND-1 and COX-IV genes to represent mtDNA and nuclear DNA, respectively.

16.2.6 Aim 2 Data, Images, and Biospecimens Used from the APS Consortium

Clinical data including syndromic phenotype (ARDS, pneumonia, sepsis), presence/type of infection, risk factors for ARDS, demographic information, comorbidities, severity of illness, physiologic data, and outcomes (survival, duration of organ support) will be utilized from each participant's inpatient admission. Long term outcomes including measures of functional status, quality of life, emotional health, cognitive performance, and respiratory symptoms at 3, 6, and 12 months will also be tested outcomes, and will be adjusted for metrics of pre-illness health. Images from the inpatient stay or the longitudinal 12-month visit will be utilized, and from longitudinal muscle ultrasound, will be used.

Biological samples will include the plasma drawn at 0, 2, and 6 days, as well as 90 days. Depending on findings, additional timepoints including d180 and d360 may be assayed for leading candidate markers. In addition, whole blood gene expression from the PAXgene RNA-stabilizing tubes will be utilized for the clustering aim.

16.2.7 Aim 2 Statistical Analysis

It is recognized that methods for analysis continue to be developed. A detailed SAP will be generated before analysis begins, in which we will specify the method considered optimal at the time or, if an optimal method cannot be easily determined, competing methods will be compared. The following outlines a general approach that might be considered for this aim.

Unadjusted tests for association between individual markers and outcomes (mortality, organ failure, or post-ICU health state) might be conducted as a t-test or Wilcoxon rank sum test as appropriate to the data distribution. Marker concentrations can be transformed for normality as needed and then used in multivariable regression analysis controlling for factors that might act as confounders (including but not exclusive to age, sex, pulmonary versus non-pulmonary source of infection, presence of sepsis, and risk factors or comorbidities). A directed acyclic graph (i.e., DAG) will be derived by the study team to guide the analysis.

Longitudinal data might use a ‘joint longitudinal and time-to-event’ model, with a longitudinal model appropriate for the outcome distribution (e.g., logistic, linear, negative binomial), and a competing risk accelerated failure time model for dropout (e.g., death, moribund, lost). The shared parameter specification can be selected for each outcome based on model fit.

Multiple methods can be enacted for clustering, and consistency across methodologies will be assessed. For example, we may employ agglomerative hierarchical clustering, Wald’s clustering, and uniform manifold approximation and projection (UMAP), and other potentially informative clustering approaches to visually inspect data.^{18–20} Within the UMAP space, we can visualize the overall gradient, or contribution, of specific biologic features using a feature-weighted kernel density weighting as we have previously published.¹⁸ Latent class modeling can also be accomplished,¹⁶ and the number of classes tested by Vuong-Lo-Mendell-Rubin test. Longitudinal data can be incorporated into longitudinal clustering by growth mixture modeling or a 2-step approach with growth curve modeling and K-means.²¹ Once we have established discernable and reproducible clusters, we can then use regression modeling to test the association between cluster and organ failure, mortality, and disability scores (CNS Vital Signs, WHODAS II, and HADS).

As discussed in the protocol, the SAP will be written and filed centrally *a priori*. If there are competing, plausible approaches, these will be compared. Adjustments to pre-specified plan will be documented with rationale. The SAP will follow the principles outlined in the protocol.

16.2.8 Aim 2 Adequacy of sample size

The statistical approaches that will be used in the ultimate analysis will be specified *a priori* in a Statistical Analysis Plan. Here, we provide an assessment of the adequacy of the sample size based on reasonable assumptions, recognizing that the final methods will be highly optimized using rapidly developing methodology.

With continuous traits such as plasma protein or nucleic acid quantification, we will have ample power to test for associations with mortality (estimated 30%), specific organ failure (estimated 10 – 40%), or specific post-ICU health impairment (estimated 30%) with the targeted deep phenotyping sample size of 1000-1500 participants at inpatient timepoints and approximately 600 participants at day 90 (3 months). This sample size will also provide adequate power to test for statistical interaction with APS state or other clinical or biological states such as sex, or race/ethnicity. This sample size will also facilitate the ability to preserve cohort participants in the remaining n=2500 of the APS cohort as a validation set for findings identified in the first n=1500 (as a secondary validation procedure to the cross-validation described in Section 12).

For clustering analyses, prior published experience in critical illness phenotypes has successfully identified between 2 and 4 biologic clusters using sample sizes ranging from n=265 to n=1200.^{14–17} With 1500 we expect adequate power for clustering with up to 150 features (more if dimension reduction is employed) as described in the rationale for the cohort sample size.

16.2.9 Aim 2 Expected Output

With this careful characterization of vascular, DAMP, and immune plasma protein and whole blood gene expression profiling across 1500 participants from the APS cohort, we anticipate:

- the generation of multivariable models including both clinically-derived and lab-derived variables that display predictive value for ARDS, AKI, 28-day mortality, and overall change in SOFA score
- the identification of plasma or gene expression features that will enhance prediction of post-APS cognitive or functional health impairments
- that better classification of the specific vascular health or DAMP signaling dysregulation across APS states, and a careful mapping of their trajectories, will suggest new therapeutic strategies
- that specific vascular, DAMP, or whole blood gene expression features will be informative to integrated subphenotype classification, and that such features can be leveraged to test for heterogeneous treatment effect in future trials

16.3 Appendix C (Aim 3): Test the hypothesis that sampling the airspaces of mechanically ventilated patients with ARDS, pneumonia and sepsis will uncover novel APS phenotypes and endotypes and inform our understanding of central mechanisms that drive short- and long-term outcomes, including pulmonary dysfunction.

16.3.1 Aim 3 Background and Rationale

ARDS and pneumonia are diseases of the lungs. Similarly, up to 50% of severe sepsis cases result from lower respiratory tract infections. Compared to the bloodstream, the luminal compartment of the lungs has been largely understudied. Moreover, despite the fact that studies of airspace biology in ARDS have yielded novel mechanistic insights,¹ phenotypes identified in ARDS patients are predominantly driven by markers of systemic inflammation and coagulation rather than respiratory variables, and airspace biomarkers were not included in the models.² There are few published studies that have sought to determine whether the previously derived hyper- and hypoinflammatory phenotypes are mirrored in airspace biology and available evidence suggests that airspace phenotypes are discordant with systemic phenotypes.^{3,4} Taken together, these factors have limited our ability to identify APS phenotypes and represent a major barrier in the field.

A new method for serially sampling the airspace in mechanically ventilated patients using fluid that condenses on the heat moisture exchanger (HME) filter has recently been described. This method is completely non-invasive, inexpensive, requires minimal investigator time and can be done serially and safely over the course of mechanical ventilation.^{5,6} We have prospectively enrolled over 400 mechanically ventilated patients at Vanderbilt in HME filter fluid studies and we have implemented this method in NHLBI-funded studies at multiple sites including University of Colorado, University of Washington, Stanford and UCSF. Moreover, we have demonstrated that protein biomarkers can reliably be measured in HME filter fluid collected from mechanically ventilated patients with ARDS and other causes of acute respiratory failure.^{5,6}

Non-bronchoscopic bronchoalveolar lavage (NBBAL) is a well-recognized approach that enables sampling of the distal airways and airspaces of individuals that are on mechanical ventilation. The technique involves instillation of saline into the distal airspaces, followed by gentle aspiration. Accordingly, cells, bacteria, lipids and proteins from the distal airspaces can be sampled. NBBAL is minimally invasive and has been demonstrated to be safe in critically ill participants.⁷

The overarching goal of this scientific aim is to test the hypothesis that sampling the airspaces of mechanically ventilated patients with ARDS, pneumonia and sepsis using HME filter fluid and NBBAL will uncover novel APS phenotypes and endotypes and inform our understanding of central mechanisms that drive short- and long-term clinical outcomes, including pulmonary dysfunction.

16.3.2 Aim 3 Study Objectives

Primary objectives (Aim 3):

1. Identify acute phenotypes of APS in mechanically ventilated patients using bulk RNA sequencing of mononuclear cells isolated from NBBAL and identify their association with short-term and long-term clinical outcomes.
2. Identify acute phenotypes of APS in mechanically ventilated patients using a panel of protein biomarkers measured in exhaled breath condensate obtained from HME filters on day 1 of mechanical ventilation along with clinical respiratory variables and identify their association with short-term and long-term clinical outcomes.

Secondary objectives (Aim 3):

1. Use longitudinal collection of HME filter fluid to determine whether phenotypes identified at the onset of acute respiratory failure are stable over time and whether new respiratory phenotypes emerge.
2. Determine which biologic processes in the airspaces are reflected in the bloodstream and which processes are lung-specific by comparing bulk RNA sequencing of mononuclear cells from blood and lungs and proteins measured in HME fluid and plasma.
3. Determine whether phenotypes derived from lung compartment biomarkers improve the ability to predict clinical outcomes versus currently accepted phenotypes defined from blood markers alone.

16.3.3 Aim 3 Study Population

All mechanically ventilated patients enrolled in APS will be eligible for inclusion if mechanical ventilation is initiated during the period of in-hospital biospecimen collection. We estimate that 1500 of the 4000 patients enrolled in the APS study will be mechanically ventilated during the first four study days.

16.3.4 Aim 3 Study Design

Prospective observational cohort study

16.3.5 Aim 3 Study Procedures

HME filter fluid studies:

After passing a safety screen to rule out severe hypoxemia ($FiO_2 > 80\%$) or high PEEP (>15 cm H₂O), HME fluid will be collected on days 0, 2, 4, 6 and 14 if patient is mechanically ventilated by placing a fresh Airlife HME filter in the ventilator circuit for 4 hours. Patients who are intubated prior to enrollment will have the first (day 0) sample collected on the day of enrollment. The Airlife HME filter is optimal for these studies, with a small dead space volume and a reliable HME fluid yield of ~1-2 ml after a 4-hour dwell time.⁵ At study sites where heated ventilator circuits are routinely used, the heated circuit will be removed or turned off for the 4-hour HME dwell time. Once removed, HME filters will be centrifuged to collect exhaled breath condensate which will be frozen in small aliquots.

A panel of protein biomarkers representing key facets of lung pathology during acute respiratory failure will be measured in duplicate in HME samples including IL-6, IL-8, TNFR1, MCP1, RAGE, SP-D, Angiopoietin-2, ICAM-1, procollagen peptide-3, protein C, PAI-1 and total protein.

NBBAL studies:

All patients that are initiated on mechanical ventilation will be considered for NBBAL. Ideally, NBBAL will be performed within 24 hours of initiation of mechanical ventilation. However, we recognize that this might not be feasible for all participants. Therefore, NBBAL may be performed as late as 96-hours after initiation of mechanical ventilation. Safety criteria for NBBAL include $FiO_2 \leq 75\%$, $PEEP < 15$, $INR \leq 3.0$, and platelets $> 50,000 / \text{ul}$. All must be met at the time of the procedure. Prior to performing NBBAL, the patient is placed on 100% FiO_2 for 10 minutes. BAL is performed using a flexible 16 gauge catheter that is gently advanced through the endotracheal tube to “wedge” the distal tip of the catheter. Serial aliquots of saline are instilled into the catheter and then aspirated. The maximum instillation volume is 120 ml.

Aspirated BAL fluid will be pooled and placed in a sterile collection container and kept on ice until processing. BAL fluid will be run through a 70 micron strainer to remove mucus and debris. Fluid will be centrifuged to pellet cells. Cell-free fluid is gently aspirated and aliquoted for banking. Cells will be washed once, and then preserved for RNA sequencing studies.

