Blood collection (phlebotomy)	Pain at phlebotomy site, infection at the phlebotomy site, bleeding, damage to surrounding nerves, transient light-headedness, fainting/syncope.	Only study or clinical personnel trained in phlebotomy will collect blood for this study. Patients will be positioned in a safe location for phlebotomy, such as supine in a bed or sitting in a chair. When possible, blood will be collected from pre-existing vascular catheters and timed with blood draws for clinical care to avoid additional phlebotomy.
Urine collection	No plausible risks identified.	Only study or clinical personnel trained in the collection of urine will collect urine for this study. Urine will be collected via patient voiding or collection from pre-existing urinary catheters. No invasive procedures will be initiated in the study to collect urine.
Collection of oral, nasal, and rectal swabs	Localized transient irritation, pain, and/or bleeding may occur at the swab site.	Only study or clinical personnel trained in the collection of oral, nasal and rectal swabs will collect swabs for this study. Personnel will be trained to hold pressure on the swab site if it bleeds.
Stool collection	No plausible risks identified.	Stool will only be collected via participants freely stooling or via stool collection systems in place for clinical care (e.g., rectal tube, fecal incontinence bag). No invasive procedures will be initiated by the study to collect stool.
HME (ventilator) filter collection	Inadvertent disconnection of ventilator tubing for longer than necessary to collect the filter, which could rarely result in low oxygen levels, organ damage, and death if not recognized. The risk of patient injury from HME (ventilator) filter collection is considered very low.	Only study or clinical personnel trained in the collection of HME (ventilator) filters will collect the filters. Ventilators at all study sites have alarms that alert clinical teams when ventilator tubing is disconnected. HME filters are routinely used for clinical care. Patients receiving invasive mechanical ventilation are routinely disconnected from the ventilator in clinical care daily. When possible, HME filters will be collected during a disconnection of the ventilator that is occurring as part of clinical care.

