For the purposes of this study, an adverse event is considered related to study procedures if there is a "reasonable possibility" of a causal relationship between a study procedure and the adverse event or the relationship cannot be determined; this includes events that are classified as definitely related, possibly related, or of uncertain relationship.

(iv) Adverse events of special interest (AESIs)

An adverse event of special interest (AESI) is defined as a pre-specified event of scientific or medical concern that has the potential of being related to study procedures and is important to understand regardless of investigator classifications. In this trial, AESIs listed below will be recorded as an AE and will require a written narrative regardless of a site's study team classification of seriousness and relatedness. For this study, the following events are AESIs:

- **AESI #1**: New or worsening hypoxemia within 30 minutes of a study-specified NBBAL. For AESI consideration, new or worsening hypoxemia is defined by the event meeting both of the following criteria: (i) a decrease in SpO₂ by at least 10 percentage points in the time window between the beginning of the procedure and 30 minutes after the procedure is completed; and (ii) a persistent absolute increase in FiO₂ by at least 10% for at least 6 hours after the procedure compared to before the procedure.

(v) Unanticipated Problem (UP)

[figure not shown]
An unanticipated problem is a finding discovered during the conduct of the study that suggests participation in the study may have more risk than was anticipated at the time of study initiation. UPs have the potential to change the risk: benefit balance of the study compared to what was known at the time of study launch.

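### The master text and Table 13 describe HME collection as taking a filter out; section 16.3.5 describes a screened 4-hour study change to the ventilator circuit, and the passages need reconciling

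*Protocol*

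**What the plan says.** **Aim 3 appendix.** Section 16.3.5 describes a timed procedure, carried out by "placing a fresh Airlife HME filter in the ventilator circuit for 4 hours". It is repeated: "HME fluid will be collected on days 0, 2, 4, 6 and 14 if patient is mechanically ventilated". It is preceded by a check on FiO2 and PEEP: "After passing a safety screen to rule out severe hypoxemia" or high PEEP. Where heated circuits are routine, "the heated circuit will be removed or turned off for the 4-hour HME dwell time". The chosen filter is described as one "with a small dead space volume and a reliable HME fluid yield".

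**Master text.** Section 8.2.2 lists HME filter fluid as a specimen from invasively ventilated patients. The only safety screen it sets out is for NBBAL. The footnotes to Tables 7 and 8 give invasive mechanical ventilation as the sole condition for HME collection.

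**Risk table.** The Table 13 row for HME filter collection (section 13.1) names one hazard: "Inadvertent disconnection of ventilator tubing for longer than necessary to collect the filter". It rates the risk of injury as very low. The measures it lists are trained staff, ventilator alarms, the routine clinical use of HME filters, the fact that ventilated patients are disconnected daily in ordinary care, and timing: "When possible, HME filters will be collected during a disconnection of the ventilator that is occurring as part of clinical care".

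**Pregnancy.** Section 7.1.3 limits pregnant participants to procedures that are not greater than minimal risk. Table 8 keeps HME collection for them at all five in-hospital time points.

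**Event collection.** Section 14.2.1 collects events that are serious and study-related, events of special interest, and unanticipated problems, and no others. The one event of special interest in section 14.2.2 is "New or worsening hypoxemia within 30 minutes of a study-specified NBBAL".

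**The concern.** The document gives two accounts of one procedure. Table 13 and the master text read as the retrieval of a filter, where the only exposure is the moment the tubing is open. Section 16.3.5 describes a study-imposed circuit configuration lasting 4 hours, which at some sites replaces the usual humidification.

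This is more than detail left to an appendix, because of how the protocol divides its own authority. Sections 3.1 and 3.2 say that the master text governs specimen collection, and that the appendices describe the analyses made with the specimens. A site that follows section 8.2.2 and the schedule tables would therefore collect HME fluid from any invasively ventilated participant, without the screen that section 16.3.5 requires first. A reader of Table 13 would weigh a risk row that does not describe the 4-hour exposure.

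The only HME risk description in this document is also the one available for judging whether collection in pregnant participants is minimal risk.

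**Working it through.** No sample size, power or error rate is involved. The check sets the passages side by side and then takes the scale from Table 9.

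**1. Element by element**

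| Element | 16.3.5 | 8.2.2 | Tables 7 and 8, footnotes | Table 13, HME row |
|---|---|---|---|---|
| Study places a fresh filter | Yes | No | No | No |
| 4-hour dwell | Yes | No | No | No |
| Heated circuit removed or turned off | Yes, where routine | No | No | No |
| FiO2/PEEP screen before placement | Yes | No (NBBAL screen only) | No (ventilation only) | No |
| Disconnection at collection | Not discussed | No | No | Yes, the only hazard |

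The single hazard in Table 13 is one that section 16.3.5 does not discuss, and every element of section 16.3.5 is missing from the other three places.

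**2. A further sign that the screen has not reached the master text.** Table 9 describes the NBBAL count as participants who are intubated, passed the safety screen and consented. It describes the HME counts only as participants on invasive ventilation. At every time point they equal the tracheal aspirate counts, for which no such screen is described. The projection appears to make no allowance for participants who fail the HME screen.

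**3. Scale, from the HME row of Table 9**

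- Collections: 1333 (Day 0) + 1233 (Day 2) + 800 (Day 4) + 600 (Day 6) + 200 (Day 14) = 4,166.
- Dwell time: 4,166 × 4 h = 16,664 h.
- Maximum per participant: 5 × 4 h = 20 h.
- Relative to NBBAL, which has its own screen in section 8.2.2 and its own event of special interest: 4,166 / 700 = 5.95.

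Table 9 calls its numbers approximate, and if the screen excludes some participants the total will be lower. The protocol does not give the share of collections at sites with heated circuits, so the number of heated-circuit changes can only be bounded at 0 to 4,166.

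**4. What event collection captures.** Under section 14.2.2 an event counts as related if it is definitely related, possibly related or of uncertain relationship. A serious event during the dwell with any of these classifications is recorded, as is an unanticipated problem. A non-serious event during the dwell, such as a transient fall in saturation (an illustration, not an event the protocol reports), would not be recorded unless it amounted to an unanticipated problem. Hypoxemia after NBBAL that meets the stated definition is recorded whatever its seriousness or relatedness.

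**The case against.** The strongest reply is that the procedure is benign, already safeguarded and already overseen. Section 16.3.1 describes HME sampling as non-invasive and safe to repeat, and cites more than 400 ventilated patients enrolled in earlier HME studies at one centre. Section 16.3.5 applies a respiratory screen and calls the dead space small. Table 13 does say that HME filters are in routine clinical use. Where a patient already has an HME filter, the study's filter may simply replace it. Section 14.2.1 limits adverse event collection on purpose, because events in this population are numerous.

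Most of this stands, and it rules out three stronger readings that a reader might infer.

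- **That the exposure is not monitored.** Serious events with a definite, possible or uncertain relationship to any study procedure are collected, as are unanticipated problems. The coordinating center reports them to the single IRB and NHLBI within 7 days of site awareness (section 14.2.3), and the OSMB reviews safety (section 14.3). What is absent is collection targeted at HME.
- **That participants are misinformed, or that the minimal-risk judgement is unsound.** The consent documents are not in the reviewed text and Protocol B is a separate document. Either may describe the dwell. No passage says that HME was kept for pregnant participants because of the Table 13 row.
- **That the dwell causes particular harms.** The documents report none, and their only statement on dead space is favorable.

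The reply does not remove the mismatch. The screen is a real safeguard, but it stands only in the appendix. Routine use of HME filters also does not describe sites where a heated circuit is the routine and the study withdraws it for 4 hours.

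**Conclusion.** The point holds as an inconsistency with a safety consequence. The governing text and the risk table omit the 4-hour dwell, the heated-circuit change and the pre-placement screen that section 16.3.5 sets out. A site working from the master text alone would not apply the screen. The mismatch touches about 4,166 planned collections, and the number that involve a heated circuit cannot be determined from the protocol.

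The conclusion rests on two assumptions: that sites treat the master text as the governing instruction, as sections 3.1 and 3.2 say, and that Table 9 is a fair projection. Operating procedures, consent documents and Protocol B could narrow the practical gap, but they cannot be seen here. The finding does not show that HME sampling is unsafe. It should be corrected, but it does not bear on the validity of the Aim 3 analyses.

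**What to change.** 1. Reconcile section 8.2.2, the footnotes to Tables 7 and 8, Table 13 and section 16.3.5 so that they describe the same procedure and the same screen. The content of the screen is for the sponsor to settle.
2. Restate the Table 13 HME row so that the risk assessment covers the 4-hour dwell and the heated-circuit change as well as the disconnection.
3. Have the sponsor confirm that the consent documents, Protocol B and the minimal-risk rationale, including the one for pregnant participants, match the procedure actually performed.
4. Record dwell start time, dwell stop time and heated circuit yes/no on the specimen form, so that the exposure can be counted and any event placed in time against it.

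Whether to add an HME-specific reportable event is for the sponsor and the OSMB to decide. Across about 4,166 dwells in ventilated patients, an event without a quantitative definition could produce many reports and would work against the restrained approach of section 14.2.1.

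The cost is single-IRB re-review of the wording and three case report form fields.
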